6.7.5 Determination of the MTD

The MTD is defined as the dose at which 30% of subjects experience a DLT during the first cycle. At each dose level, MTD will be estimated based on actual observations from subjects to construct a dose and toxicity rate model using the maximum likelihood method. As data accumulate and the reassessment continues, the MTD will be determined based on the convergence criteria described in Section 5.6.4. The recommended Phase 2 dose (RPTD) will be defined by observed DLTs and/or determination of MTD.

8.0 Statistical Methods and Determination of Sample Size

8.1 Statistical and Analytical Plans

Unless otherwise noted, for all statistical analyses, statistical significance will be determined by a two-sided p-value < 0.05 .

8.1.1 Demographics and Treatment Allocation

Demographics

Descriptive statistics will be provided for baseline demographic variables for the Phase 1 and the Phase 2a portion of the study separately. Age, height and weight will be summarized with means, medians, standard errors, standard deviations and ranges. Frequencies and percentages will be provided for gender and race.

Treatment Allocation

One of the objectives of the Phase 1 portion of this study is to determine the MTD, and the dose allocation process will be conducted according to a continual reassessment method (CRM).^{35,36,37} A two-parameter logistic regression model will be employed to characterize dose and toxicity rate relationship. A prior model based on preclinical and clinical data will be employed to estimate doses with approximately 30% and 90% probability of inducing a DLT. The MTD is the dose that reflects a 30% rate of DLT. The dose associated with 90% DLT rate will be incorporated for future model fitting to stabilize the high dose-toxicity portion of the model. For each subject, the response will be defined as 0 (no DLT event) or 1 (DLT). Along with the actual observed data, 10 imputed subjects will be added with 9 subjects having DLT and 1 without DLT at the dose associated with 90% DLT rate. A small weight of 0.025 will be assigned to these imputed data to reflect a small degree of certainty, and at the same time to stabilize the model fitting process as shown in the simulations. To estimate the dose corresponding to approximately 30% probability of inducing DLT, one out of the three subjects in the 160 mg dosing cohort from the M06-814 study will be utilized with a small weight of

0.083 assigned to these prior data. For the actual observations, a unity weight will be assigned. The maximum likelihood method will be employed to estimate the parameters and probability of DLT within the framework of the logistic regression analysis. The fitted model will be inverted to estimate the target dose associated with 30% chance of DLT, or the MTD. The next cohort of subjects will then be assigned to the projected MTD and evaluated. The outcome will be incorporated to update the logistic regression model using all the cumulative information. The design will continue to adapt data from current results and assign subjects to the projected MTD until the target dose changes by less than 10%, or a sample size of 40 subjects is reached. Simulations to compare the conventional fixed 3+3 design and the CRM based design are provided in [Appendix F](#).

8.1.2 Pharmacokinetics

8.1.2.1 Tabulations and Summary Statistics

Plasma concentrations of ABT-263 and pharmacokinetic parameter values will be tabulated for each subject and each dose level, and summary statistics will be computed for each sampling time and each parameter.

8.1.2.2 Model and Tests

Dose Proportionality

For subjects who participate in the Phase 1 14/21 day dosing portion of the study, an analysis will be performed on pharmacokinetic variables for C1D1 dose to simultaneously explore for demographic variables that explain some of the variability in pharmacokinetics and to address questions of dose proportionality and linear kinetics. An analysis will be performed for dose-normalized C_{max} , T_{max} , and dose-normalized AUC_t (AUC_{0-24}), provided that they can be adequately determined from the data. The model used for the statistical analyses will include dose level. This may be done by classifying subjects by dose level or, if appropriate, using dose level as a continuous variable. Covariates such as age, body weight, body surface area, gender, and potentially formulation (if applicable), as well as others that might explain some of the variability in

the population will be included in the model initially. However, a covariate may be dropped from the model if the regression coefficient is not significant at level 0.10. The natural logarithmic transformation will be employed for C_{\max} and AUC_t unless the data clearly indicate that other transformation or the untransformed variable provides more nearly symmetric probability distributions and/or more nearly homogenous variances across dose levels. Within the framework of the model, tests that have good power for a trend with dose will be performed on the effect of dose level.

A corresponding analysis will also be performed on pharmacokinetic variables of the dose on C1D14 for both the Phase 1 14/21 and 21/21 day dosing schedules. The variables will include dose-normalized C_{\max} , T_{\max} , and dose-normalized AUC_t (AUC_{0-8}).

Additional analyses will be performed if useful and appropriate.

8.1.2.3 Missing Values and Model Violations

The possibility of bias from missing data of subjects who prematurely discontinue will be addressed. Normally values of pharmacokinetic variables (C_{\max} , AUC , etc.) will be determined without replacing missing individual concentration values, simply using the available data, and if necessary doing the analysis with some missing values for a pharmacokinetic variable. However, missing concentration values for isolated individual blood samples may be replaced (imputed) if such might affect study conclusions or meaningfully affect point estimates.

8.1.3 Exploratory Efficacy

The following exploratory efficacy analyses will be performed on the data collected from the Phase 2a portion of the study.

8.1.3.1 Progression-Free Survival

The distribution of PFS will be estimated using Kaplan-Meier methodology. Median time to PFS and the corresponding 95% confidence interval will be estimated.

For a given subject, PFS will be defined as the number of days from the date the subject started study drug to the date the subject experiences an event of disease progression, as defined in Section 5.3.3, or to the date of death if disease progression is not reached. All events of disease progression will be included, regardless of whether the event occurred while the subject was still taking study drug or had previously discontinued study drug. Events of death will be included for subjects who had not experienced disease progression provided the death occurred within 2 cycles (42 days) of the date of the last available tumor evaluation. If a subject has not experienced an event of disease progression or death as defined above, then the subject's data will be censored at the date of the last available evaluation for disease progression. The date of the last available evaluation will be the date of the last study visit at which a tumor assessment was performed.

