Note: A schedule of assessments for subjects enrolled in Phase 1 – 14/21 Day Dosing can be found in [Table 1](#). A schedule of assessments for subjects enrolled in Phase 2a can be found in [Table 3](#). Pharmacokinetic (PK) collection time points for Phase 1 are located in [Table 4](#) and [Table 5](#). PK collection time points for Phase 2a are located in [Table 6](#). Biomarker collection time points for Phase 1 are in [Table 8](#). Biomarker collection time points for Phase 2a are in [Table 9](#).

Table 3. Schedule of Assessments (Phase 2a) –21/21 Day Continuous Dosing Schedule with Lead-in Period

Procedure	Screening ^a	LD1	LD2	LD3	C1 D1	C1 D2	C1 D3	C1 D15	Weekly Through C2	D1 of Each Cycle After C2 ^b	End of Every 3 rd Cycle	C5 D1	C9 D1	Final Visit ^s	30 Day Safety Follow-Up ^s	Post-Treatment
Informed Consent	X															
Physical Exam (including weight)	X ^c	X			X				X ^d	X				X	X	
Medical History	X	X														
Oncologic History	X															
Vital Signs	X	X			X				X	X				X	X	
12-lead ECG ^e	X							X				X	X	X		
2D Echocardiogram with Doppler ^f	X							X				X	X	X		
Platelet Count ^g	X	X	X	X	X	X	X	X	X	X		X	X	X	X	
Lymphocyte Enumeration ^h	X							X			X			X		
Pregnancy Test ⁱ	X	X														
Chemistry ^j	X	X	X	X	X	X	X		X	X				X	X	
Hematology ^j	X	X	X	X	X	X	X		X	X				X	X	
Urinalysis ^j	X	X			X				X	X				X	X	
Performance Status (ECOG)	X	X			X				X	X				X	X	
Tumor Assessments ^k	X ^l										X ^{m,n}			X		
Bone Marrow Aspirate/Biopsy ⁿ	X ^o															
Clinical Disease Progression Assessment					X					X				X		
Adverse Event/Concomitant Medications Assessment	X ^p	X			X			X	X	X				X	X ^q	

Table 3. Schedule of Assessments (Phase 2a) – 21/21 Day Continuous Dosing Schedule with Lead-in Period (Continued)

Procedure	Screening ^a	LD1	LD2	LD3	C1 D1	C1 D2	C1 D3	C1 D15	Weekly Through C2	D1 of Each Cycle After C2 ^b	End of Every 3 rd Cycle	C5 D1	C9 D1	Final Visit ^s	30 Day Safety Follow-Up ^s	Post-Treatment
Dispense Meds/Subject Dosing Log		X			X				X	X						
Collect Unused Study Drug									X	X				X		
Survival Assessment(s) ^t																X

C = Cycle; D = Day; L = Lead-in

- Screening procedures must be performed within 14 days prior to study drug administration, except baseline tumor assessment scans (if clinically indicated) and bone marrow aspirate/biopsy, which must be performed within 21 days prior to study drug administration.

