 - j. The specific laboratory tests required for chemistry, hematology and urinalysis are listed in [Table 7](#). Triglycerides will only be collected at Screening and at the Final Visit. Amylase and lipase will be collected at Screening, Cycle 1 Day 15, and Final Visit. For any subjects who are at high risk for tumor lysis syndrome (TLS) during Cycle 2 and beyond, additional samples for hematology and chemistry may be collected as per the management guidelines in Section [6.7.4](#).
 - k. Assessment for tumor response will be performed at the end of Cycle 2, end of Cycle 4, end of every 4 cycles through Cycle 20 (i.e., C8, C12, C16, C20), end of every 8 cycles thereafter (i.e., C28, C36, C44. . .) and at the Final Visit. Analysis of peripheral blood for tumor response will be performed on Day 1 (pre-dose) of the following cycle for every tumor assessment.
 - l. A CT scan will be performed at Screening (within 21 days prior to study drug administration).
 - m. Assessments for tumor response will be repeated 2 months after NCI-WG (1996) criteria for a complete remission (CR) are first met and/or at least 2 months after IWCLL updated NCI-WG (2008) criteria for a complete remission (CR or CRi) or partial remission (PR) are first met.
 - n. If clinical and laboratory criteria for a CR or PR are met), a bone marrow aspirate/biopsy and CT scan should be performed at least 2 months after the criteria are first met in order to confirm a CR or PR. A bone marrow aspirate/biopsy will be performed at the end of Cycle 8 (for all subjects regardless of response) if the subject is continuing to receive ABT-263.
 - o. Bone marrow aspirate/biopsy will be done at Screening (within 21 days prior to study drug administration) unless a bone marrow aspirate and biopsy was obtained within 12 weeks of starting study drug without intervening treatment and is representative of the subject's existing disease.
 - p. Serious adverse event assessment will be performed at Screening after informed consent has been obtained.
 - q. Adverse events will be followed until satisfactory clinical resolution of the adverse event is achieved.
 - r. Survival assessments will be collected every 3 months for 2 years following discontinuation from the study (including the extension portion of the study). In Protocol Amendment #12 this information will no longer be collected.

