5.3.3.1.3 Definition of Clinical Disease Progression (Phase 2a)

Clinical disease progression is defined as determined by the investigator only, which may be characterized as, but is not limited to:

- Constitutional symptoms attributable to CLL progression (e.g., unintentional weight loss, significant fatigue [e.g., ECOG performance score ≥ 2], persistent fevers without signs of infection or night sweats)
- Requirement for palliative radiation, chemotherapy, surgery, immunotherapy or biologics
- Death from disease progression

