In the event that a subject withdraws or is discontinued from the study, reason(s) for the discontinuation from the study will be recorded. A physical examination, ECG, echocardiogram, vital signs measurement, laboratory analyses, performance status assessment, collection of unused study drug, an assessment of adverse events and tumor assessment (if needed) will be performed as soon as possible after discontinuation from the study.

A Safety Follow-up Visit should be performed for all subjects approximately 30 days following discontinuation of ABT-263 and then as clinically appropriate for safety assessment. The subject will be followed until a satisfactory clinical resolution of the adverse event(s) is achieved. If the subject refuses a follow-up visit or the visit is not performed, the reason should be noted in the subject's source documentation.

In the event of a positive pregnancy test for a subject during the study, the administration of study drug to that subject must be discontinued immediately. The investigator will report the positive pregnancy test result by telephone within 1 working day to the contact listed in Section 6.5.

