For subjects who participated in the Phase 1, 14/21 day dosing portion of the study, an analysis was performed on pharmacokinetic variables for Cycle 1 Day 1 dose to simultaneously explore for demographic variables that explained some of the variability in pharmacokinetics and to address questions of dose proportionality and linear kinetics. An analysis was performed for dose-normalized C_{max} , T_{max} , and dose-normalized AUC_t (AUC_{0-24}). The model used for the statistical analyses included dose level. This was done by classifying subjects by dose level. Covariates such as age, body weight, BSA, gender, and formulation, as well as others that might have explained some of the variability in the population, were considered for inclusion in the model initially. However, a covariate was dropped from the model if the regression coefficient was not significant at level 0.10. The natural logarithmic transformation was employed for C_{max} and AUC_t . Within the framework of the model, tests that had good power for a trend with dose were performed on the effect of dose level.

A corresponding analysis was also performed on pharmacokinetic variables of the dose on Cycle 1 Day 14 for both the Phase 1, 14/21 and 21/21 day dosing schedules. The variables included dose-normalized C_{max} , T_{max} , and dose normalized AUC_t (AUC_{0-8}).

Exploratory Efficacy

The following exploratory efficacy analyses were performed for Phase 1 and Phase 2 of the study. Unless specified otherwise all the analyses were presented by dose levels and overall; all the response and associated data were evaluated based on NCI WG Criteria (1996), and updated IWCLL NCI WG Criteria (2008) for Phase 1, and 2, respectively.

Progression-Free Survival

The distribution of PFS was estimated using Kaplan-Meier methodology. Median time to PFS and the corresponding 95% confidence interval were estimated.

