For a given subject, PFS was defined as the number of days from the date the subject started study drug to the date the subject experiences an event of disease progression, or to the date of death if disease progression was not reached. All events of disease progression were included, regardless of whether the event occurred while the subject was still taking study drug or had previously discontinued study drug. Events of death were included for subjects who had not experienced disease progression provided the death occurred within 2 cycles (42 days) of the date of the last available tumor evaluation. If a subject had not experienced an event of disease progression or death as defined above, then the subject's data was censored at the date of the last available evaluation for disease progression. The date of the last available evaluation was the date of the last study visit at which a tumor assessment was performed.

Response Rate

- Objective Response Rate (ORR)
 - Phase 1: $ORR = CR + PR$.
 - Phase 2: $ORR = CR + CR_i + PR$.

- Best Response Rate
 - Phase 1: Complete Response (CR), Partial Response (PR), Stable Disease (SD), Disease Progression (PD), and Incomplete Data (ID) were reported.
 - Phase 2: Complete Response (CR), Complete Response - incomplete bone marrow (CRi), Partial Response (PR), Stable Disease (SD), Disease Progression (PD), and Incomplete Data (ID) were reported.
- Disease Control Rate (DCR)
 - Phase 1: $DCR = CR + PR + SD$.
 - Phase 2: $DCR = CR + CRi + PR + SD$.

The exact binomial distribution was used to construct this confidence interval for the response rates, and the corresponding 95% confidence interval was constructed.

Time to Tumor Progression

Time to tumor progression for a given subject was defined as the number of days from the date the subject started study drug to the date of the subject's tumor progression. Time to tumor progression was collected up to 2 cycles (42 days) following the date of the last available tumor evaluation. All events of tumor progression were included, regardless of whether the event occurred while the subject was still taking study drug, or after the subject discontinued study drug. If a subject had not progressed, then the data was censored at the date of the last study visit at which a tumor assessment was performed.

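### The 42-day limit on counting deaths in PFS is shorter than the scheduled 84- and 168-day gaps between tumor assessments, so some deaths in subjects with no missed visit are censored, which in most scenarios biases exploratory PFS upward

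*Protocol*

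**What the plan says.** Protocol 8.1.3.1 includes a death without progression as a PFS event "provided the death occurred within 2 cycles (42 days) of the date of the last available tumor evaluation". Any other subject without a counted event is censored at the last evaluation, which the section defines: "The date of the last available evaluation will be the date of the last study visit at which a tumor assessment was performed". The SAP, under Progression-Free Survival, repeats the rule ("Events of death were included for subjects who had not experienced disease progression provided the death occurred within 2 cycles (42 days") and applies PFS to both Phase 1 and Phase 2. The planned summary is the median: "Median time to PFS and the corresponding 95% confidence interval were estimated".

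The assessment schedule is in footnote k to protocol Tables 1, 2 and 3 and under Tumor Assessments in 5.3.1.1. Assessments fall at the end of Cycle 2, the end of Cycle 4, then "end of every 4 cycles through Cycle 20 (i.e., C8, C12, C16, C20), end of every 8 cycles thereafter", and at the Final Visit. A cycle is 21 days (5.1).

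Three other places bear on the point:

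- Table 3 has a separate row, "Clinical Disease Progression Assessment", on Day 1 of each cycle after Cycle 2.
- Protocol 5.3.3.1.3 lists "Death from disease progression" as a form of clinical progression, for Phase 2a only.
- Protocol 5.4.1 says that a "tumor assessment (if needed) will be performed as soon as possible after discontinuation from the study".

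**The concern.** A limit on how long after the last assessment a death may count normally deals with subjects who missed assessments, whose progression status before death is unknown. Here the limit is shorter than the planned gap between assessments for most of the schedule. It therefore removes deaths in subjects who did everything the protocol asked.

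Death is a component of PFS. Moving such a death back to the last assessment and calling it censored is informative censoring: the subject leaves the risk set because of the event being measured. The expected direction is a PFS curve that is too high. PFS is a named objective of the Extension (protocol 4.0) and is reported with a confidence interval for 29 Phase 1 and 31 Phase 2 subjects.

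**Working it through.** **The plan's own figure.** 2 cycles × 21 days = 42 days, as stated.

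**Uncovered share of each on-schedule gap** = (gap − 42) / gap.

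- C2 to C4: 2 × 21 = 42 days; 0 uncovered.
- C4 to C8, and each gap to C20: 4 × 21 = 84 days; 42 uncovered (50%).
- After C20: 8 × 21 = 168 days; 126 uncovered (75%).

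**First gap (screening scan to end of C2).** The scan may be 0 to 21 days before first dose.

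- 14/21 dosing: the end of C2 is day 42, so the gap is 42 to 63 days with 0 to 21 uncovered. A day-0 scan leaves it fully covered.
- With the planned 7-day lead-in: the end of C2 is day 49, so the gap is 49 to 70 days with 7 to 28 uncovered.

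**Total to the end of C20.** Four 84-day gaps give 4 × 42 = 168 uncovered days.

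- Lead-in: 168 + 7 to 28 = 175 to 196 of 427 days (41% to 46%).
- 14/21: 168 + 0 to 21 = 168 to 189 of 420 days (40% to 45%).

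These are shares of calendar days, not of deaths.

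**Illustrative size.** The documents give no event rates, so the following is assumption. Kaplan-Meier simulation used the Phase 2a schedule, exponential times, a screening scan 10 days before first dose, no missed visits, no discontinuation and no deaths classed as progression. With assessment never stopping, counting all deaths is a fair reference here.

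| Median to progression / to death (days) | Deaths without detected progression that are censored | 24-month PFS, all deaths → 42-day rule | Median PFS (days) |
|---|---|---|---|
| 365 / 730 | 51% | 16.2% → 23.4% | 259 → 343 |
| 365 / 1,460 | 54% | 22.6% → 27.4% | 343 → 343 |
| 365 / 2,920 | 56% | 27.2% → 30.0% | 343 → 343 |
| 730 / 730 | 55% | 28.5% → 41.0% | 388 → 595 |
| 730 / 1,460 | 60% | 40.0% → 48.4% | 595 → 595 |
| 730 / 2,920 | 62% | 47.8% → 52.6% | 595 → 763 |

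The rule raised 24-month PFS in all six, by 2.8 to 12.5 points, and raised the median in three.

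**Relaxing the assumptions.** The first two cases are measured against a reference in which assessments continue after stopping and all deaths count.

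- Stopping at 20% to 40% per year, independent of death, with deaths known for 30 days after stopping: 32% to 54% of deaths without documented progression are censored. The 24-month excess is 0.4 to 6 points if deaths are 15% to 30% of first events, and 5 to 11 points if they are 50%.
- Half of deaths counted through 5.3.3.1.3 and half of progressions caught at Day 1 checks: 16% to 27% censored; −0.2 to +4.2 points.
- Half of deaths falling within 30 days after a Final Visit assessment: 17% to 31% censored; roughly −1 to +5 points.

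**The planned summary.** Across 36 scenarios with stopping (two schedules; median 6, 12 or 24 months; deaths 15%, 30% or 50% of first events; 20% or 40% stopping per year), the median is within 7 days of the reference in 10. Otherwise it rises, for example from 406 to 427 days, and at most from 763 to 1,099. In single trials of 31 subjects (five scenarios, 42-day rule against a window equal to the interval), the median moves 7 days or less in 37% to 74% of trials in which it is reached. A typical 95% interval at a 12-month median is 219 to 595 days.

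**The case against.** **Limited consequence.** PFS is exploratory (protocol 5.3.3), single-arm and untested, and the sample size (8.2) does not rest on it. Only the median and its interval are planned, and sampling error at n = 31 exceeds the shift. All of this stands. It limits the importance of the point but does not remove a bias built into the definition.

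**Other assessments restart the window.** A Final Visit tumor assessment does so, although 5.4.1 asks for it only if needed. If deaths cluster soon after stopping, many are counted. Response-confirmation assessments (notes m and n, at least 2 months after criteria are first met) also shorten gaps: a repeat at day 60 of an 84-day gap leaves 60 − 42 = 18 uncovered days instead of 42. Both stand and reduce the size.

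**Day 1 clinical progression checks.** On the literal text these do not restart the window, because 8.1.3.1 ties the date to a tumor assessment and Table 3 lists the two on separate rows. They still detect some progressions, leaving fewer deaths without documented progression.

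**Deaths from CLL already count.** In Phase 2a this is arguable: 8.1.3.1 points to 5.3.3, which contains 5.3.3.1.3. The SAP's PFS definition drops that pointer, 5.3.3.1.3 does not cover Phase 1, and deaths from other causes remain exposed.

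**Early deaths are failures under 8.1.3.7.** That section classifies response; it does not define PFS events.

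**Every third cycle.** The tumor-assessment column heading in Tables 1 to 3 differs from footnote k. A 63-day gap would still leave 21 days uncovered.

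**Stronger readings a reader might infer.** One is that the reported PFS is known to be materially too high. The documents give no rates, and some plausible assumptions put the error near zero. Another is that counting every death gives the correct PFS. No scheduled tumor assessments follow discontinuation, while Phase 2a deaths could be known for up to 2 years (until Amendment 12), so late deaths would pull PFS down.

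**Conclusion.** The mismatch is certain and follows from the documents' own figures: the window is 42 days, and the scheduled gaps are 84 and then 168 days. The C2 to C4 gap, and the first gap on 14/21 dosing with a day-0 scan, are fully covered; the later gaps are not. Deaths on uncovered days are censored at the last assessment.

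The direction is upward in most scenarios, and in every one with no stopping. The size is not determined. It depends on death, progression and stopping rates, on how closely deaths follow a Final Visit assessment, on confirmation assessments, and on whether 5.3.3.1.3 deaths count. About 0.7 to 2.6 points of downward error at 24 months arises under any window, because subjects who stop without progression are censored at the Final Visit.

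This should be fixed in reporting. It changes no test, sample size or trial decision.

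**What to change.** The SAP describes analyses already done, so add to the 42-day result rather than replace it.

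1. Report a PFS analysis, labelled post hoc and shown beside the 42-day result, in which a death without documented progression is an event on its date if it falls within the scheduled interval in force at the last tumor assessment: 42 days after C2, 84 days from C4 until C20, 168 days from C20. The first interval runs from the screening scan to the end of C2.
2. After discontinuation no further assessment is due, so run the window from the Final Visit assessment, using the interval last in force.
3. Give the number of deaths that each rule censors.
4. State in the SAP whether deaths under 5.3.3.1.3 are progression events.
5. State whether the Extension's progression checks every 4 cycles count as tumor evaluations. Appendix G puts them on a separate row, with tumor assessments only at the Final Visit. If they count, use 84 days there.
6. If an all-deaths version is shown, do not present it as unbiased.

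The cost is SAP wording and a Kaplan-Meier re-run on death dates already used for overall survival. PFS may look shorter. In the simulations, an interval-based window has no error without discontinuation. With deaths known for 2 years after stopping, its 24-month error is −0.6 to −2.9 points, against −0.4 to −8.6 for counting all deaths. It was further from the reference than the 42-day rule in 6 of 36 scenarios (deaths 15% of first events, 40% per year stopping). Disclose that late deaths without further assessments can bias this version downward.
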